Ixabepilone BMS-247550 CA163-157 Clinical Protocol

TMHRI IRB#0908-0265 BMS Protocol #: CA163-157

ICE Trial

RANDOMIZED OPEN-LABEL NEO-ADJUVANT PHASE II STUDY COMPARING IXABEPILONE (I) VS IXABEPILONE PLUS CETUXIMAB (IC) IN TRIPLE NEGATIVE BREAST CANCER PATIENTS (ICE)

VERSION: 8.0 DATE: 8/9/2012 PHASE: II IND Number: 104,307

[name]. Director, Methodist Cancer Center The Methodist Hospital/Weill Cornell University [name] [contact] [contact] [contact]

STUDY SUMMARY

Title:	Randomized open-label neo-adjuvant phase II study comparing					
	ixabepilone (I) vs. ixabepilone plus cetuximab (IC) in Triple negative breast					
	cancer patients					
Objectives:	Primary Objective:					
	1. To determine the pathologic complete response rate (pCR) (breast and					
	axilla) of Ixabepilone versus Ixabepilone when combined with cetuximab					
	in patients with invasive breast adenocarcinoma T1N1-N3M0 or					
	T2-4 N0-3M0 disease who are Triple negative and who are candidates for					
	preoperative chemotherapy.					
	Secondary Objective(s):					
	1. To evaluate overall objective response rate in both treatment groups.					
	2. To assess toxicity of each regimen.					
	Exploratory Objectives:					
	1. To correlate the expression of biomarkers such as PTEN, EGFR					
	and EGFR-pathway associated genes (including, but not limited to,					
	TGF- α , CRYAB, NRAS, KRAS, AKT3, PTEN, MEK1 and KRAS					
	amplicon genes) with the objective clinical and pathologic response.					
	2. To potentially explore other gene/protein expression patterns,					
	mutations and gene/chromosomal copy number alterations related					
	to sensitivity or resistance to ixabepilone, other anti-microtubule					
	agents and cetuximab. These additional exploratory analyses may					
	include, but are not limited to, beta tubulin isoforms, ABC					
	transporters, TACC3, HCAPG, GTSE1, Kallikreins and defined					
	gene models associated with ixabepilone response.					

Study	-Patients with either T1N1-N3M0 or T2-4 N0-3M0 disease who are Trip				
population:	on: negative and who are candidates for preoperative chemotherapy.				
Sample	116 patients.				
Size:					
Number of	Single Institution: The Methodist Hospital Research Institute.				
Centers:					
Treatment	This is a randomized open-label phase II trial; 116 triple negative breast				
Plan:	cancer patients will be randomized equally between 1) Ixabepilone or				
	2) Ixabepilone plus Cetuximab.				
	The study population will include subjects ≥ 18 years of age diagnosed				
	with invasive ductal carcinoma (IDC). Randomization will be stratified by				
disease stage (T1N1-3M0 or T2-4 N0-3M0).					
	Prior to randomization, all patients will have a physical assessment,				
	imaging, a blood draw, and a diagnostic biopsy prior to the start of				
	treatment.				
	The study doctor will determine if the subject qualified to be enrolled in this				
	study. If subjects are enrolled, the duration of their participation is				
	expected to be approximately 6 months				
	Treatment Arm 1				
	Patients will receive Ixabepilone 40mg/m ² given over approximately				
	3-hours on day 1.				
	Patients will receive a total of four cycles of this drug with each cycle				
	given 21 (+/- 3) days.				
	Subjects will be premedicated approximately 1 hour before the ixabepilone				
	infusion with 1) both an oral H1 blocker (diphenhydramine 50 mg or				
	equivalent) and an oral H2 blocker (e.g., ranitidine 150 300 mg or				
	cimetidine 300–800 mg or nizatidine 150-300 mg or famotidine 20–40 mg);				

	or 2) with premedication per institutional standards.			
	Premedication with steroids is indicated in subjects who developed a			
	hypersensitivity reaction to ixabepilone in previous cycles. Patients with			
	severe reaction (see dose modification chart below)should not be			
	retreated.			
	Treatment Arm 2			
	Patients will receive Ixabepilone 40mg/m ² given over approximately			
	3-hours on day 1followed by cetuximab given on day 1 at 400 mg/m ² as			
	an initial loading dose (first infusion) administered as approximately a			
	120-minute IV			
	infusion (maximum infusion rate 5 mL/min) followed by 250 mg/m ²			
	infused over approximately 60 minutes (maximum infusion rate 5 mL/min) as			
	subsequent weekly dose.			
	Patients will receive a total of 4 cycles of this combination with each			
	cycle being 21 (+/-2) days.			
	Subjects will be premedicated approximately 1 hour before the ixabepilone			
	infusion with either 1) both an oral H1 blocker (diphenhydramine 50 mg or			
	equivalent) and an oral H2 blocker (e.g., ranitidine 150-300 mg or			
	cimetidine 300–800 mg or nizatidine 150 - 300 mg or famotidine			
	20–40 mg); or 2) with premedication per institutional standards.			
	Premedication with steroids is indicated in subjects who			
	developed a hypersensitivity reaction to ixabepilone in previous cycles.			
	Patients with severe reaction (see dose modification chart below)should			
	not be retreated.			
	Subjects who are to receive cetuximab are to be premedicated with an			
	H ₁ antagonist (e.g., 50 mg of diphenhydramine IV or equivalent).			
Inclusion	Inclusion Criteria:			
Criteria:	Patients with histologic confirmation of invasive breast carcinoma.			
	 Patients must have intact primary tumor. 			
	Patients must have intact primary tumor.			

	 Patients ≥ 18 years.
	 Invasive breast carcinoma must be determined to be ER (-), PR (-)
	and HER2Neu (-) prior to study entry.
	 Patients should have T1N1-3M0 or T2-4 N0-3M0.
	 Patients with bilateral breast cancer are eligible.
	 Patients with second primary breast cancers are eligible.
	 Patients should have a Karnofsky performance scale of ≥ 70%.
	 Patients must have clinically measurable disease by physical exam
	to be treated in the neoadjuvant setting.
	 Patients should have adequate bone marrow function, as defined
	by peripheral granulocyte count of ≥1500/mm³, and platelet count
	≥10000mm ³ .
	 Patients must have adequate liver function with a bilirubin within
	normal laboratory values. Alkaline phosphatase and transaminases
	(ALT and AST) may be up to 1.5 x upper limit of normal (ULN) of
	the institution.
	 Patients should have adequate renal function with creatinine levels
	within normal range.
	 Patients should have a normal left ventricular ejection fraction
	(LVEF) of ≥ 50%.
	 Negative serum or urine pregnancy test for a woman of childbearing
	potential (WOCBP).
	WOCBP must use a reliable and appropriate contraceptive method
	during the study and six months after chemotherapy is completed.
	WOCBP are women who are not menopausal for 12 months or had
	no previous surgical sterilization.
	 Patients must sign an informed consent indicating that they are
	aware of the investigational nature of the study, in keeping with
	institutional policy
Exclusion	Exclusion Criteria:
Criteria:	 Patients with a history of other invasive malignancies diagnosed

	and treated within the previous 5 years, except non-melanoma skin					
	cancer and non-invasive cervical cancer.					
	 Her2Neu, ER and PR positive patients should be excluded. 					
	 Patients with an organ allograft or other history of immune 					
	compromise.					
	• Prior treatment with any investigational drug within the preceding 4					
	weeks.					
	 Chronic treatment with systemic steroids or another 					
	immunosuppressive agent.					
	Uncontrolled chronic viral infections or patients requiring parenteral					
	antibiotics will be excluded. Patients taking highly active anti-viral					
	therapies and with controlled disease will be allowed to participate.					
	Patients with an active, bleeding diathesis or on oral anti-vitamin K					
	medication (except low dose coumarin defined as 1 mg a day)					
	Other concurrent and/or uncontrolled medical disease which could					
	compromise participation in the study (i.e., uncontrolled diabetes,					
	uncontrolled hypertension, severe infection, severe malnutrition,					
	unstable angina, or congestive heart failure - New York Heart					
	Association Class III or IV, ventricular arrhythmias, active ischemic					
heart disease, myocardial infarction within six months, o						
	or renal disease, active upper GI tract ulceration).					
	 Patients with a pre-existing peripheral neuropathy(> grade1). 					
Statistical	Blocked randomization will be used to randomly assign patients either to					
Design:	arm 1 or arm 2. A total of 116 patients will be enrolled to allow for 6.5%					
	dropout before randomization of 108 patients, given sample size of 54					
	patients in each arm to be able to detect 25% difference in pathological					
	complete response rates between the arm with Ixabelpilone plus					
	Cetuximab and the arm with Ixabepilone with 81.9% power and a two-					
	sided significance level of 0.05.					

TMHRI Version: 8

RANDOMIZED OPEN-LABEL NEO-ADJUVANT PHASE II STUDY COMPARING IXABEPILONE (I) VS IXABEPILONE PLUS **CE**TUXIMAB (IC) IN TRIPLE NEGATIVE BREAST CANCER PATIENTS (ICE).

Randomized open-label neo-adjuvant phase II study comparing ixabepilone (I) vs. ixabepilone plus cetuximab (IC) in Triple negative breast cancer patients.

0.0 STUDY SUMMARY	2
0.0 Schema	7
1.0 Synopsis	11
1.1 Primary Objective(s)	11
1.2 Secondary Objective(s)	11
1.3 Exploratory Objective (s)	12
2.0 Study Flow chart or Schedule of Events	14
2.1 Study Procedures by Visit and Treatment Cycle	16
2.2 Screening/Baseline visit	16
2.2.1 Radiological Evaluation Visit	17
2.3 Cycle 1 Clinic Visit	17
2.3.1 Cycle 1 Post-Infusion Laboratory Visits	18

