2.0 Study Flow chart or Schedule of Events

Procedure	Screening/Baseline Visit	Prior to Each Cycle	End-of- Treatment Visit ^a	Follow-up
Eligibility Assessments				
Obtain Informed Consent	Х			
Confirm Inclusion/Exclusion Criteria Met ^b	Х			
Obtain Medical History	Х			
Safety Assessments				
Karnofsky performance scale ^{a b}	Х	Х	Х	
Record Weight and Height	Х	Х	Х	
Document Vital Signs	Х	Х	Х	
Assess Signs and Symptoms and Adverse Events $^{\rm c,o}$	Х	Х	Х	
Perform Pregnancy Test in WOCBP ^d	Х			
Perform mammogram ^e	Х		Х	
Perform ultrasound of breast and nodal region ^e	Х		Х	
(MRI)*				
Perform Laboratory Tests ^{fghi}	Х	Х	Х	Х
Prepare Paraffin Block/Slides ^j	Х		Х	
Obtain Blood Sample for biomarkers ^k **	Х		Х	
Perform Electrocardiogram	Х		Х	
Perform Echocardiogram ¹	Х			
Efficacy Assessments				
Evaluate Tumor Response RECIST Criteria ^m	Х		Х	
Clinical Drug Supplies				
Premed Before Infusion ⁿ		Х		

TMHRI Version: 8

a. Evaluate subjects who discontinue the protocol for reasons other than disease progression every 4 weeks until progression or until they receive additional anti-cancer therapy.

b. Karnofsky Performance Status of =/> 70% is required for study entry.

c. Document signs and symptoms and adverse events at least every 4 weeks until all study drug-related toxicities resolve, stabilize, return to baseline, or are deemed irreversible.

d. Pregnancy tests (serum or urine) should be performed within 72 hours of study start, or whenever pregnancy is suspected.

e. Mammogram and ultrasound should have been performed any time within 90 days prior to beginning of the study treatment and within 3 to 4 weeks of the neoadjuvant therapy completion before surgery. *MRI (magnetic resonance imaging) should be performed only if requested by the physician.

f. Laboratory tests comprise albumin, alkaline phosphatase, ALT, AST, total bilirubin, blood urea nitrogen, calcium, chloride, creatinine, glucose, lactic dehydrogenase, magnesium (at baseline only for the ixabepilone alone arm), potassium, phosphorus, and sodium, as well as complete blood count (Hemoglobin, Hematocrit, RBC, WBC, Platelets) with differential (Neutrophils, Lymphocytes, Monocytes, Eosinophils, Basophils). CrCL "CrCl = [(140 - age) x IBW] / (Scr x 72) (x 0.85 for females)" before every cycle for patients with an abnormal creatinine.

g. Perform laboratory tests within 72 hours of beginning each cycle. Perform baseline laboratory tests within four (4) weeks before administration of study drug

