6.0 Study Population

-Patients with either T1N1-N3M0 or T2-4 N0-3M0 disease who are triple negative and who are candidates for preoperative chemotherapy.

Patients will receive a physical assessment, imaging, a blood draw, and a biopsy prior to the start of treatment.

6.1 Inclusion Criteria:

-Patients with histologic confirmation of invasive breast carcinoma.

-Patients must have intact primary tumor.

-Age \geq 18 years.

-Invasive breast carcinoma must be determined to be ER (-), PR (-) and

HER2Neu (-) prior to study entry.

-Patients should have T1N1-3M0 or T2-4 N0-3M0.

-Patients with bilateral breast cancer are eligible.

-Patients should have a Karnofsky performance scale of \geq 70%.

-Patients must have clinically measurable disease by physical exam to be treated in the neoadjuvant setting.

-Patients should have adequate bone marrow function, as defined by peripheral granulocyte count of \geq 1500/mm³, and platelet count \geq 100000mm³.

-Patients must have adequate liver function with a bilirubin within normal laboratory values. Alkaline phosphatase and transaminases (ALT and AST) may be up to 1.5 x upper limit of normal (ULN) of the institution.

-Patients should have adequate renal function with creatinine levels within normal range.

-Patients should have a normal left ventricular ejection fraction (LVEF) of ≥50%.

-Negative serum or urine pregnancy test for a woman of childbearing potential (WOCBP).

-WOCBP must use a reliable and appropriate contraceptive method during the study and six months after chemotherapy is completed. WOCBP are women who are not menopausal for 12 months or had no previous surgical sterilization. -Patients must sign an informed consent indicating that they are aware of the investigational nature of the study, in keeping with institutional policy.

6.2 Exclusion Criteria:

-Patients with a history of other invasive malignancies diagnosed and treated within the previous 5 years, except non-melanoma skin cancer and non-invasive cervical cancer.

-Her2Neu, ER and PR positive patients should be excluded.

-Patients with an organ allograft or other history of immune compromise.

-Prior treatment with any investigational drug within the preceding 4 weeks.

-Chronic treatment with systemic steroids or another immunosuppressive agent.

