Because clinical trials are conducted under widely varying conditions, the adverse reaction rates observed in the clinical trials of a drug cannot be directly compared to rates in other clinical trials and may not reflect the rates observed in clinical practice. Unless otherwise specified, assessment of adverse reactions is based on one randomized study (Study 046) and one single-arm study (Study 081). In Study 046, 369 patients with metastatic breast cancer were treated with Ixabepilone 40 mg/m² administered intravenously over 3 hours every 21 days, combined with capecitabine 1000 mg/m²twice daily for 2 weeks followed by a 1week rest period. Patients treated with capecitabine as monotherapy (n=368) in this study received 1250 mg/m² twice daily for 2 weeks every 21 days. In Study 081, 126 patients with metastatic or locally advanced breast cancer were treated with Ixabepilone 40 mg/m² administered intravenously over 3 hours every 3 weeks. The most common adverse reactions ($\geq 20\%$) reported by patients receiving Ixabepilone were peripheral sensory neuropathy, fatigue/asthenia, myalgia/arthralgia, alopecia, nausea, vomiting, stomatitis/mucositis, diarrhea, and musculoskeletal pain. The following additional reactions occurred in $\geq 20\%$ in combination treatment: palmarplantar erythrodysesthesia (hand-foot) syndrome, anorexia, abdominal pain, nail disorder, and constipation. The most common hematologic abnormalities (>40%) include neutropenia, leukopenia, anemia, and thrombocytopenia. NCI CTC grading for febrile neutropenia ranges from Grade 3 to 5. Three patients (1%) experienced Grade 5 (fatal) febrile neutropenia. Other neutropenia-related deaths (9) occurred in the absence of reported febrile neutropenia. Peripheral sensory neuropathy (graded with the NCI CTC scale) was defined as the occurrence of any of the following: areflexia, burning sensation, dysesthesia, hyperesthesia, hypoesthesia, hyporeflexia, neuralgia, neuritis, neuropathy, neuropathy peripheral, neurotoxicity, painful response to

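### Version 8.0 gives two platelet minimums for entry, 10,000 in the Study Summary and 100,000 in section 6.1, and does not say which list governs

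*Combined protocol and SAP*

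**What the plan says.** **Platelet minimum.** The Study Summary, under Inclusion Criteria, defines adequate marrow function "by peripheral granulocyte count of ≥1500/mm³, and platelet count", and the next line gives the platelet figure as at least 10000. Section 6.1 requires "adequate bone marrow function, as defined by peripheral granulocyte count of" at least 1500/mm³, with platelets of at least 100000. Both lists print the platelet unit as mm³ without the slash. Both are operative Version 8.0 text, not a record of superseded wording.

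**Which list applies.** The Study Summary's Treatment Plan entry says "The study doctor will determine if the subject qualified to be enrolled in this" study, and names no list. The schedule of events in section 2.0 has a row "Confirm Inclusion/Exclusion Criteria Met" without a section reference. The footnote on that row, footnote b, restates one criterion only: "Karnofsky Performance Status of =/> 70% is required for study entry". Sections 2.2 and 2.3 make randomization follow confirmation of eligibility, again without naming a list.

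**Other platelet threshold.** A footnote to the hematologic dose-modification table in section 7.3.1 holds ixabepilone, after the listed platelet toxicities, until the count reaches 100,000/mm³.

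**Baseline laboratory tests.** Footnote g of the schedule says "Perform baseline laboratory tests within four (4) weeks before administration of study drug". Section 2.2 likewise allows screening procedures, blood work included, up to four weeks before therapy. Section 2.3 accepts cycle 1 baseline tests only if obtained within two weeks, and section 2.7.1 also sets two weeks. On the pre-cycle rule, footnote g says "Perform laboratory tests within 72 hours of beginning each cycle" with no exception. Section 2.3 exempts cycle 1, and section 2.7.1 limits the rule to subsequent cycles.

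**The concern.** An entry laboratory limit has to give the same answer whichever page the screening staff open. Here it does not. The Study Summary is not a short abstract pointing to section 6: it contains complete inclusion and exclusion lists that a site could screen from.

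Nor can one list be assumed to mirror the other, because they differ elsewhere. The Summary makes patients with second primary breast cancers eligible, and section 6.1 has no such line.

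What is at stake is safety at enrolment. Section 10.1 says that the most common hematologic abnormalities "include neutropenia, leukopenia, anemia, and thrombocytopenia". As written, a patient can be enrolled properly under the Summary and still be ineligible under section 6.1. The investigator, a monitor and an auditor could each reach a different answer on whether that enrolment was a deviation.

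**Working it through.** No figure in the plan needs reproducing for this point. The check sets the texts side by side and takes the ratio and the width of the disagreement.

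**Step 1: the two entry criteria**

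| | Study Summary, Inclusion Criteria | Section 6.1 |
|---|---|---|
| Granulocytes | ≥1500/mm³ | ≥1500/mm³ |
| Platelets | ≥10000 | ≥100000 |

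The granulocyte limit agrees, so this is one criterion stated twice with one number changed.

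**Step 2: size of the conflict**

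- Ratio: 100000 / 10000 = 10.
- Width of the band: 100000 − 10000 = 90000 per mm³.
- Below 10,000 a patient fails both lists, and at 100,000 or above a patient meets both. From 10,000 to just under 100,000 the lists give opposite answers.

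**Step 3: search for a rule that settles it**

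- The Summary's Treatment Plan entry leaves qualification to the study doctor and names no list.
- The eligibility row in section 2.0 names no section, and footnote b covers Karnofsky status only.
- Sections 2.2 and 2.3 refer to eligibility in general terms.
- The section 7.3.1 footnote (100,000/mm³) governs resumption of ixabepilone after platelet toxicity. It is not an entry criterion.

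No precedence rule was found anywhere in the document, and no third entry value.

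**Step 4: effect on the statistical design**

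The sample-size calculation in section 12.1 uses an 18% pCR rate in Arm 1, a 25-point difference, 54 patients per arm and a two-sided 0.05 level. No platelet value enters it. The documents give no platelet distribution, so the number of patients in the band cannot be computed.

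**Step 5: the separate laboratory-window item**

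| Place | Baseline window | 72-hour rule |
|---|---|---|
| Section 2.0, footnote g | 4 × 7 = 28 days | each cycle, unqualified |
| Section 2.2 | 4 × 7 = 28 days | not stated |
| Section 2.3 | 2 × 7 = 14 days (cycle 1) | cycle 1 exempt |
| Section 2.7.1 | 2 × 7 = 14 days | subsequent cycles only |

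Two places give four weeks and two give two weeks. Tests drawn 15 to 28 days before the first dose (28 − 14 = 14 days of disagreement) are acceptable under footnote g's baseline window and section 2.2, and too old under sections 2.3 and 2.7.1. Under section 2.3 the consequence is that the test is repeated; the patient is not excluded.

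**The case against.** The strongest objection is that the conflict turns on a single zero and may not be on the printed page. The Summary table was damaged in reading elsewhere, with clipped words, a repeated bullet and a line cut off in the exclusion criteria. This stands as a reason to look at the source page before anything else. It does not remove the point: the supplied platelet line shows no gap, and the granulocyte figure on the line above is intact.

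A second objection is that this is an obvious slip between a synopsis and the body. A reader might go further and infer that the section 6.1 figure must be the intended one, because the dose-delay footnote in section 7.3.1 uses the same number. The documents do not support that inference. The footnote concerns resumption after toxicity, and no text links it to entry. Even an evident slip in a safety criterion needs correcting, so that staff do not have to guess.

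Third, the practical exposure may be small. Both lists exclude active bleeding diathesis and uncontrolled concurrent disease, which gives some protection but does not replace a count. The thrombocytopenia statement in section 10.1 comes from studies in metastatic or locally advanced disease, one of them with capecitabine. In the neoadjuvant study CA163-080 (section 4.0.2), thrombocytopenia appears as a serious event in 1 of 161 subjects, but that study's platelet entry limit is not given. This is fair context and a good reason not to claim a number of patients harmed. It does not make the two lists agree.

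**Conclusion.** The contradiction is real in the text as supplied and should be fixed. Two current inclusion lists set platelet minimums that differ tenfold, they disagree over a band 90,000/mm³ wide, and no rule chooses between them. It is an internal inconsistency in an enrolment safety threshold, not a flaw in the statistical design.

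The conclusion rests on two assumptions: that the Summary figure was read correctly from the source page, and that the unit in both lists means per mm³. The tenfold ratio does not depend on the second.

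Three stronger readings are not supported:

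- A reader might infer that patients with low counts were or will be enrolled. The documents contain no enrolment data and no platelet distribution.
- A reader might infer that the trial's power or primary comparison is compromised. Neither uses the platelet limit.
- A reader might take footnote g as the lone outlier on the laboratory window. It is not, because section 2.2 gives the same four weeks.

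The laboratory-window item is minor. The need to amend rests on the platelet conflict alone.

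**What to change.** 1. Check the source page of the Study Summary for the printed platelet figure. If it matches section 6.1, the platelet item closes.
2. If it reads as supplied, reconcile the Study Summary and section 6.1 to one platelet minimum. The sponsor decides the value, and this review does not propose one.
3. State which criteria list governs enrolment, and cite that section in the eligibility row of the section 2.0 schedule.
4. Minor: reconcile section 2.0 footnote g and sections 2.2, 2.3 and 2.7.1 on the baseline laboratory window, and footnote g with sections 2.3 and 2.7.1 on whether the 72-hour rule covers cycle 1. Changing footnote g alone would leave section 2.2 in conflict with sections 2.3 and 2.7.1.

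The cost is an administrative amendment: one figure, one governing statement, and wording in up to four places for the laboratory items. The sample size and analysis do not change. At most, the laboratory wording that is adopted determines whether some baseline blood tests have to be repeated.
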